- Gross non-compliance with protocol: The medical monitor or investigator may request permanent study discontinuation in the event of a major protocol deviation such as administration of prohibited concomitant medication, lack of cooperation, or noncompliance.

Endpoints for Evaluation:

Primary:

The primary endpoint is the combined incidence of either DSA or IA on peripheral blood molecular profiling at one year or at the conclusion of the study. For this purpose, DSA will be considered as a categorical (binary) variable with positivity determined at a threshold criteria approaching MFI = 1000 at any time during the study. For reporting purposes, IA will be considered either present or absent using the Trugraf™ v2.0 molecular assay. For the purposes of the study, a negative designation (Trugraf TX Normal) will be referred to as Immune Quiescence (IQ). Due to operating characteristics of the assay, a positive designation will be considered evidence of Immune Activation (IA) in all patients.

The modified Full Analysis Set (mFAS) will be used for the primary endpoint analysis.

Secondary:

The assessment and comparison of the incidence of DSA between treatment groups will rely on the binary variable of DSA positivity at a threshold criteria approaching an MFI of 1000. Comparisons of the cohorts with respect to the various molecular designations as well as correlating the results with DSA will rely on the categorical (binary) variable of positivity using the Trugraf™ v2.0 molecular assay.

Comparisons between treatment cohorts regarding incidence will rely upon assessments for each of the following results at any point in the study:

- DSA
- IA)
- TG
- Acute and chronic forms of ABMR
- C1q-binding DSA
- HLA-DQ DSA
- DSA IgG₃ isotype
- Required antibody reduction

- eGFR at various thresholds (less than 30, 40, and 50 mL/min/1.73 m²) and whether a five-point decline in eGFR occurs
- Graft loss (defined as subject death, retransplantation, transplant nephrectomy, or a return to dialysis for at least a 6 week duration)
- Death
- BPAR (inclusive of ABMR and TCMR)
- Loss to follow-up

Time-to first occurrence will be assessed for each of the following: DSA, HLA-DQ DSA, C1q-binding DSA, DSA IgG3 isotype, IA, TG, select BANFF histology grades (acute and chronic forms of ABMR, acute and chronic active TCMR, borderline changes, and IFTA), mortality, and local BPAR.

The frequency of the type of antibody reduction employed will be assessed.

Patient MFI and eGFR values will be assessed over time.

Assessments of histopathology in biopsies will be made using the following endpoints:

- Incidence of ci, ct, and ptc scores greater than one
- Biopsy scores for g, t, v, i, cg, ct, ci, cv, ah, ptc, and mm

The safety endpoint for AEs will be the incidence of each type of AE based on system organ class and using the preferred term from the most recent version of the Medical Dictionary for Regulatory Activities (MedDRA).

Persistence of DSA and IA will be additional endpoints for comparisons in patients who develop IA and DSA on molecular profiling.

Exploratory:

- The incidence of a second two-part composite endpoint encompassing the incidence of acquiring DSA or positive evidence of TG on a centrally-interpreted biopsy during the first year post-transplant or by the conclusion of the study
- Expression results, mapped to known immunological pathways implicated in immune-mediated, kidney transplant tissue injury.
- With appropriate informed consent, long-term graft and patient survival in study participants by future linking to the Scientific Registry of Transplant Recipients (SRTR) following completion of ASTOUND.
- The economic burden of treating patients with molecular evidence of immune activation and DSA formation may be assessed using Medicare claims data (or commercial payer cost data in patients required to transfer from Medicare to private insurance).
- Time to first DSA or IA positive test results
- Outcomes in like patients between cohorts managed with maintenance protocol biopsy vs. biopsy for cause with respect to the composite endpoint, the components thereof, complications, and resource utilization.

Statistical Methods:

Sample Size Justification:

The sample size for this study was determined based upon a comparison of the rate of the two-part composite endpoint in the Astagraf XL group compared to the immediate-release tacrolimus group. Assuming a rate of 20% would be observed for the immediate-release tacrolimus group compared to a rate of 10% for the Astagraf XL group, 220 subjects per group are needed to achieve an 80% power to detect a difference between Astagraf XL and immediate-release tacrolimus with a two-sided alpha level of 0.05. The study will enroll 275 subjects/group (550 total) to allow for 20% dropout.

Efficacy:

The analysis of efficacy will be conducted using the mFAS.

The primary efficacy endpoint is the incidence of any one of the following in the first two years post-transplant:

- DSA formation
- IA

The primary endpoint will be analyzed at a single time point per Section [7.4.1](#)

The incidence of the primary endpoint will be summarized by treatment group with frequencies and percentages. Differences between treatment groups will be analyzed using logistic regression and controlled using pre-defined covariates.

For subjects with missing or incomplete endpoint data who did not permanently switch therapy or were discontinued from the study prior to DSA/IA event (who are lost to follow up, or those who expire for any reason), negative DSA/IA values will be imputed unless there is an otherwise positive result.

The hypothesis for comparison is as follows:

- H0: The probability of incidence for the primary endpoint is the same between patients receiving Astagraf XL and patients receiving immediate-release tacrolimus.
- H1: The probability of incidence for the primary endpoint is not the same between patients receiving Astagraf XL and immediate-release tacrolimus.

Hypothesis testing will be performed using a two-sided test with a 0.05 significance level. The 95% confidence interval for the odds ratio of the primary endpoint between Astagraf XL and twice daily tacrolimus will be included.

Analyses of treatment group differences for secondary endpoints will be evaluated by time and overall. The scope of these analyses will include the following: DSA formation, IA, TG, acute and chronic forms of ABMR, C1q-binding DSA, HLA-DQ DSA, DSA IgG₃ isotype, the requirement for antibody reduction therapy, chronic graft dysfunction, graft loss, local BPAR, mortality, loss to follow-up, ordinal antibody strength, MFI score, histopathology assessments, and tacrolimus trough levels.

Pharmacokinetics:

Not applicable.

Pharmacodynamics:

Not applicable.

Safety:

Adverse events will be coded using the Medical Dictionary for Regulatory Activities (MedDRA). The number and percentage of AEs, SAEs, AEs leading to discontinuation, and AEs related to study drug will be summarized by system organ class, preferred term and treatment group. The number and percentage of AEs by severity will also be summarized. All AEs will be listed.

Interim Analyses:

Not applicable.

V. FLOW CHART AND SCHEDULE OF ASSESSMENTS

Flow Chart

[figure not shown]

Table 1 Schedule of Assessments

Study Day	Screening (-21 to 0) ¹	0 ¹	30	90	180	270	365	455 ²	545 ²	635 ²	730 ³	Unscheduled Visit ⁴	
Week	-3 to 0	0	4	12	24	36	52	64	76	88	104	n/a	
Window (days)			± 21	± 21	± 21	±21	± 21	± 21	± 21	± 21	± 21	n/a	
Screening: Inclusion/Exclusion Criteria	X												
Informed Consent/Assent	X												
Demographics & Medical History	X	X ⁵											
Height, Pre-op Weight ⁶	X												
Concomitant Medications ⁷	X	X	X	X	X	X	X	X ⁸	X ⁸	X ⁸	X ⁸	X	
Physical Exam	X												
Transplant Information and Donor Information/HLA typing ⁹		X											
Randomization ¹⁰		X											
Astagraf XL Arm: Study Drug Dispensing ¹¹		X	X	X	X	X	X	X	X	X	X		
BID Tacrolimus Arm: Study Drug Dispensing ¹²		X	→									X	
Clinical Labs Recording		X ¹³	X ¹⁴	X ¹⁴	X ¹⁴	X ¹⁴							
Kidney Biopsy Results ¹⁵		X	→									X	
Outcomes Review ¹⁶			X	X	X	X	X				X	X	
Adverse Events Recording ¹⁷		X	→									X	
Blood Samples for DSA/anti- HLA/IgG ₃ isotyping, C1q-binding DSA ¹⁸		X ¹⁹	X	X	X	X	X				X		
Blood Samples for Molecular Diagnostics ¹⁸			X	X	X	X	X				X		
Blood Sample for Potential Future Analysis (optional) ^{18, 20}			X	X	X	X	X				X		
BK Viremia Review ²¹		X	→									X	

Footnotes appear on next page

1. Per convention, Day 0 of transplant is the date of transplant completion (revascularization). Assessments may be done on day -1 for transplant procedures that span midnight. Screening and day 0 may occur on the same day. In all cases, blood obtained for baseline antibody testing must be obtained prior to surgery. For subjects that have a separate screening visit prior to day of transplant, inclusion/exclusion criteria will be reassessed prior to transplant to ensure continued eligibility.
2. Visits in 2nd year of follow-up to include quarterly drug dispensing visits for Astagraf XL cohort at which time AEs will be recorded in the eCRF. For patients receiving immediate-release tacrolimus in the control arm, AEs will be assessed by quarterly phone interview in the 2nd year and recorded in the eCRF.
3. Study visit at end of 2nd year to include measurement of DSA and molecular markers in both control and experimental groups along with the following clinical history: serum creatinine; urinary protein; interval biopsy results; and interval history of infection, BPAR, graft loss, or mortality.
4. Unscheduled visits may be performed at any time during the study whenever necessary to assess for or follow-up on adverse events, or if deemed necessary by the investigator.
5. For subjects whose screening visit occurred prior to day 0, any updates to medical history should be recorded at day 0 visit.
6. Height will only be obtained at the screening visit and dry weight will only be obtained at screening and pre-operatively on day 0.
7. Includes, but not limited to, concomitant immunosuppressant medication, tacrolimus dose/formulation(s)/manufacturer(s), recording of all anti-rejection therapy, and P₄₅₀ inducers/inhibitors.
8. For the 2nd year of follow-up, only concomitant medications administered for a corresponding AE should be recorded in the eCRF.
9. Transplant information: type of transplant (living related, living non-related, DD, and whether organ was obtained in the setting of DCD), number of prior transplants and reason for prior graft loss (if applicable), total cold and warm ischemia time in hours and minutes, donor KDPI, ABO blood typing, HLA typing of donor and recipient, degree of HLA mismatch between donor and recipient, most recent panel reactive antibody testing (most recent cPRA level), and pre-transplant MFI status. Donor viral serology information (HBV, HCV, CMV and EBV), age, sex, height, weight, donor cause of death, ethnicity, ex vivo perfusion parameters, ABO typing, and results of any pre-implantation biopsies of the donor kidney.
10. Occurs at the pre-op visit, prior to transplant, if living donor (within 7 days). Randomization to occur upon hospital admission for deceased donors or for living donor recipients whose Screening and Day 0 visit occur on the same day.
11. Astagraf XL will be supplied by Astellas and dispensed by the participating institution. At the final study visit, subjects will return unused Astagraf XL. Additional Astagraf XL will not be provided to subjects at the final study visit.
12. After discharge from the hospital, patients randomized to receive twice daily immediate-release tacrolimus will receive study-provided vouchers and will be permitted to receive any immediate-release tacrolimus product available to them through normal dispensing mechanisms. At the final study visit, subjects will return unused vouchers; following the final study visit, vouchers previously provided to the subjects will be deactivated to prevent additional use. Additional vouchers will not be provided to subjects at the final study visit.
13. Recording of hematology, serum chemistries, urinalysis (including urine protein), tacrolimus trough concentrations, HgA1c, and whole blood tacrolimus concentrations obtained per SOC. See Section [5.4.3](#) for the components of the routine clinical labs that will be recorded. For all labs except whole blood tacrolimus concentrations and creatinine, only those labs obtained closest to targeted date of visit need to be recorded. For the Day 0 visit, pre-transplant labs should be recorded. For whole blood tacrolimus concentrations, at the Day 0 and Day 30 visits, only the concentration obtained closest to the targeted date of visit needs to be recorded. For the 90, 180, 270, and 365 day visits, all available outpatient tacrolimus concentration assessments done (per SOC) and available in the centralized medical records since the previous study visit should be recorded. For creatinine assessments, the assessment done closest to the targeted date of visit (obtained per SOC) as well as an additional assessment done at least one month prior to that assessment (if obtained per SOC) will be recorded on the eCRF.

Footnotes continued on next page

14. For visits following day 365, only serum creatinine levels, urinary protein, and tacrolimus trough concentrations obtained as part of SOC should be recorded. For all labs except creatinine, only labs obtained closest to targeted date of visit need to be recorded. For creatinine assessments, the assessment done closest to the targeted date of visit (obtained per SOC) as well as an additional assessment done at least one month prior to that assessment (if obtained per SOC) will be recorded on the eCRF.
15. All kidney biopsy results obtained during the study should be recorded in the eCRF. For all participants who undergo at least one kidney biopsy during the first year post-transplant (either for cause or per institutional protocol), the kidney biopsy performed closest to the 12 month visit (but no later than 14 months post-transplant) will be submitted for central pathological grading. Additionally, de-identified copies of all kidney pathology reports must be submitted to Astellas.
16. Inclusive of patient survival status, cause of death, rejection episodes, new diagnoses, and pathology review.
17. Adverse event collection will begin once informed consent/assent has been signed and continue throughout the subject's participation in the study. All new SAEs occurring up to 7 days after the end of study visit must be reported. *Note: The transplant procedure that occurs on Day 0 is not considered an AE or an SAE.*
18. Assessed via central labs.
19. On Day 0, sample drawn prior to transplant procedure and stored to confirm pre-op DSA (will be analyzed only as needed). Sample may be drawn on Day -1 for morning transplant procedures. De-identified copies of local typing reports (for donor and recipient typing) and recent local pre-transplant DSA testing results (if performed) will also be submitted to the central lab.
20. Patients will have the option of having an additional sample collected at each phlebotomy session for storage and analysis in future trials of transplant outcomes and biomarker discovery.
21. If a subject develops clinically significant BK viremia (as assessed per SOC) during study participation, the peak viremia level obtained per SOC will be retrospectively recorded in the eCRF at the time of subject's study discontinuation or completion.

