For central laboratory analysis, initial FlowPRA[®] (One Lambda, Canoga Park, CA) screening will be used to test for the presence of anti-HLA antibodies. Once identified, single antigen testing will be used to identify DSA specificity with an MFI greater than or approaching 1000 used to determine antibody positivity. In borderline cases, a three-member adjudication board of independent, qualified HLA Lab Directors will determine positivity based on relevant clinical data. In samples that meet threshold criteria for DSA positivity, additional classification will be performed to determine the degree of antibody strength. By performing a single dilution (1:16) of DSA-containing samples, the alloimmune response can be further elucidated [Tambur et al, 2015]. Samples in which MFI disappears (becomes < 1000 MFI) will be regarded as "weak." Samples increasing to > 10,000 MFI upon dilution will be regarded as having significant prozone and will be regarded as "strong." Samples which may increase or decrease, but nevertheless remain between 1000 and 10,000 MFI will be regarded as "moderate." In certain cases, samples with evidence of fluorescence that are nevertheless below MFI criteria for DSA positivity will also be subject to dilution. Samples increasing to above threshold criteria following dilution will be regarded as positive and assumed to be under the influence of a prozone effect that impairs antibody detection. For statistical purposes, the DSA with the highest MFI level obtained during the course of the study will be used for statistical comparisons between groups. However, the strongest antibody observed at each HLA-locus will be reported separately and tracked for patients who are DSA positive [Tambur et al, 2015]. In all cases, positive DSA and/or molecular testing results will be communicated to the patient's treating physician when available (DSA) or at the end of study (molecular testing). Testing will be performed in batches. De-identified typing reports (donor and recipient) will be requested from the participating centers to inform the central laboratory testing. De-identified results of recent local pre-transplant DSA testing (if performed per SOC) will also be requested to facilitate interpretation of central DSA testing results.

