5.3 Efficacy Assessment

5.3.1 Efficacy

5.3.2 Donor Specific Antibody

Class I and Class II DSA will be assessed by a central HLA lab at 1, 3, 6, 9, 12, and 24 months in all patients, and as needed at baseline to confirm local testing results. Otherwise, initial DSA screening prior to transplant will be performed locally as per standard of care with results reported on the eCRF. For the purpose of assessing the impact of the proposed intervention (Astagraf XL vs. twice daily, immediate-release tacrolimus), detection of DSA at any time during the course of the study will be treated as a positive result. For the purposes of the study, DSA positivity will be defined at an MFI threshold approaching 1000. An independent adjudication board will take into account relevant clinical information to qualify samples in borderline cases. In cases where DSA is quantifiable, but nevertheless at an MFI < 1000, patient serum will be diluted and re-measured to mitigate the possible impact of the prozone phenomenon [Tambur et al, 2015]. Samples with new MFI levels above the target threshold will subsequently be regarded as positive.

In each case of quantifiable DSA or C1q-binding DSA at or above the MFI threshold, patient sera may be diluted 1:16 and re-assessed [Tambur et al, 2015]. MFI readings remaining above 10,000 following dilution or those increasing to over 10,000 following dilution (thus indicating prozone activity) will be regarded as “strong.” Samples with MFI values from 1000 to 10,000 will be designated “moderate.” Serum samples that demonstrate disappearance of MFI or reduction to < 1000 following dilution will be regarded as “weak.”

All borderline MFI threshold results will be reviewed by the Adjudication Board (see Section [10.2](#)) in conjunction with relevant clinical information to confirm that the results have been categorized correctly. The Adjudication Board will also 1) review and adjudicate all cases antibody formation (per central HLA lab assessment) post-transplantation and 2) determine the need for ancillary testing of pre-transplant sera in equivocal cases in which such testing could indicate the presence of pre-transplant DSA.

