10.2 Adjudication Board: MFI Adjudication Committee

An Adjudication Board will be formed to review all borderline MFI threshold results that occur during the study to confirm that the results have been categorized correctly. The Board will consist of three independent members of appropriate expertise who are not directly involved in the clinical study and who are blinded to the treatment allocation. Information related to the borderline threshold results will be sent to the committee for blinded assessment. A separate charter will describe which results will require adjudication and the specification of the result-related documents, listings, data flow, method(s) for data collection and data transfer.

The Adjudication Board will 1) review and adjudicate all cases of antibody formation (per central HLA lab assessment) post-transplantation and 2) determine the need for ancillary testing of pre-transplant sera in equivocal cases in which such testing could indicate the presence of pre-transplant DSA.

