For central laboratory analysis, initial FlowPRA[®] (One Lambda, Canoga Park, CA) screening will be used to test for the presence of anti-HLA antibodies. Once identified, single antigen testing will be used to identify DSA specificity with an MFI greater than or approaching 1000 used to determine antibody positivity. For borderline cases, a three member adjudication panel of independent, qualified, HLA Lab Directors will determine positivity based on relevant clinical data. In samples that meet threshold criteria for DSA positivity, additional classification will be performed to determine the degree of antibody strength. By performing a single dilution (1:16) of DSA-containing samples, the alloimmune response can be further elucidated. Samples in which MFI disappears (becomes < 1000 MFI) will be regarded as "weak." Samples increasing to > 10,000 MFI upon dilution will be regarded as having significant prozone and will be regarded as "strong." Samples which may increase or decrease, but nevertheless remain between 1000 and 10,000 MFI will be regarded as "moderate." In certain cases, samples with evidence of fluorescence that are nevertheless below MFI criteria for DSA positivity will also be subject to dilution. Samples increasing to above threshold criteria following dilution will be regarded as positive and assumed to be under the influence of a prozone effect that impairs antibody detection. For statistical purposes, the DSA with the highest MFI level obtained during the course of the study will be used for statistical comparisons of DSA positivity between groups. However, the strongest antibody observed at each HLA-locus will be reported separately and tracked for subjects who are DSA positive. In all cases, positive DSA and/or molecular testing results will be

communicated to the subject's treating physician when available (DSA) or at the end of study (molecular testing). Testing will be performed in batches. De-identified typing reports (donor and recipient) will be requested from the participating centers to inform the central laboratory testing. De-identified results of recent local pre-transplant DSA testing (if performed per standard of care [SoC]) will also be requested to facilitate interpretation of central DSA testing results.

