7.4.2 Analysis of Secondary Endpoints

Risk factor analysis will be conducted in two parts. First, is to identify risk factors for outcomes based on factors measured at time of transplantation (baseline) including the pre-defined stratification factors. Last, is to identify risk factors for outcomes based on factors that are measured post-randomization and therefore, are subject to change e.g., average daily dose of MPA treatment or cumulative dose of corticosteroids. All models will include randomized treatment, irrespective of statistical significance. Models to assess risk factors for binary or categorical variables will be done using logistic regression. Odds ratio and 95% CI will be used as measures of strength of association and precision, respectively.

Risk factor analyses will be conducted for eight binary variables: IFTA, IFTA and Inflammation, BPAR, the four-part traditional composite endpoint, early MMF interruption/discontinuation, and eGFR status based on three thresholds 30, 40, and 50. The biopsy data are based on the central pathology results over the course of one year plus 2 months window. eGFR status variables are based on the assessment at Day 365 visit.

Each risk factor analysis model will include treatment group and a main factor: either De novo DSA, IA, or the composite of De novo DSA and IA. Following additional covariates will be considered for the two types of models, and a multicollinearity assessment will be proceeded for the final variable selection:

Risk factors measured at time of transplantation include:

- Cold ischemic time
- Warm ischemic time

- KDPI% \leq 50% (yes/no)
- KDPI% $>$ 50% (yes/no)
- HLA Class II mismatch (yes/no)
- Donor status (living/deceased)
- Donation after circulatory death (yes/no)
- Donor Age
- Donor-Recipient sex mismatch (match/mismatch)
- Donor-Recipient race mismatch (match/mismatch)
- Preservation by cold storage (yes/no)

Post randomization risk factors include:

- Cumulative Dose of Corticosteroids
- Average daily dose of MPA
- Mean dose level of tacrolimus
- Mean tacrolimus trough level
- Number of excursions below 80% or above 120% of the average tacrolimus trough level
- IPV estimated by CV%
- Post-transplant BK virus infection

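### Neither the Protocol nor the SAP keeps graft outcomes from the Board that decides borderline DSA results, so DSA as a risk factor may be partly defined by the outcomes it is tested against

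*Protocol*

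**What the plan says.** Protocol 5.3.2 sets the cut loosely: "DSA positivity will be defined at an MFI threshold approaching 1000". No lower limit is given for what counts as borderline.

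The rule for borderline results appears in four places. The Protocol synopsis has: "In borderline cases, a three-member adjudication board of independent, qualified HLA Lab Directors will determine positivity based on relevant clinical data". Protocol 2.2.1 uses the same sentence. Protocol 5.3.2 has: "An independent adjudication board will take into account relevant clinical information to qualify samples in borderline cases". SAP 3.2 has: "For borderline cases, a three member adjudication panel of independent, qualified, HLA Lab Directors will determine positivity based on relevant clinical data". None of them lists the data allowed or excluded.

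Protocol 10.2 adds safeguards. The three members are people "who are not directly involved in the clinical study and who are blinded to the treatment allocation", and "Information related to the borderline threshold results will be sent to the committee for blinded assessment". It also refers to a separate charter that specifies which results are adjudicated and which documents are used.

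DSA is used in two ways. It is one of two components of the primary composite, with IA. SAP 7.4.2 also makes it an explanatory factor: "Each risk factor analysis model will include treatment group and a main factor: either De novo DSA, IA, or the composite" of the two. The outcomes of those models include interstitial fibrosis and tubular atrophy (IFTA), BPAR, the four-part traditional composite and three eGFR thresholds.

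SAP 7.4.1.1 attributes DSA positivity to a named transplant immunology laboratory and does not mention the Board.

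**The concern.** A risk-factor model assumes that the factor was classified without regard to the outcome. If a near-threshold antibody is more likely to be called positive because the Board can see a rejection episode, a poor biopsy or a rising creatinine, the outcome has entered the definition of the factor. The model would then show DSA associated with rejection or low eGFR even if the borderline antibodies carried no information. Blinding to allocation does not prevent this, because the leak runs through outcome and not through arm.

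The plan recognises the risk elsewhere: the central pathologist is blinded to clinical results as well as to patient identifiers (Protocol synopsis and 2.2.1). The DSA Board has no matching statement.

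At stake is the credibility of the DSA-outcome associations, which bear on the trial's rationale that DSA is a usable surrogate. A second, weaker issue is that neither document says product name or dosing frequency is removed from what the Board sees, and either would identify the arm.

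**Working it through.** **1. What is and is not withheld from the Board**

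| Item | Protocol or SAP statement |
|---|---|
| Treatment allocation | Withheld (Protocol 10.2) |
| Product, dosing frequency | No redaction stated |
| Biopsy, rejection, creatinine | Not withheld |
| IA result | Kept from investigators until study end (Protocol 8.1.1); nothing said about the Board |
| Documents in the Board's packet | Left to the charter (Protocol 10.2) |

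**2. Size of the outcome leak (illustration)**

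The documents give no borderline rate and no call rates, so every input here is an assumption:
- c = 0.08, the share of patients with clear DSA positivity
- b = 0.04 to 0.10, the share who are borderline
- h and l, the probability that a borderline result is called positive when rejection is visible and when it is not
- no true link between DSA and rejection, so c and b are the same in both groups
- the Board sees rejection status for every borderline patient who has it

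P(DSA+ | rejection) = c + b·h, and P(DSA+ | no rejection) = c + b·l. The odds ratio follows from these two.

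Worked case with b = 0.04, h = 0.7, l = 0.4: 0.08 + 0.028 = 0.108 and 0.08 + 0.016 = 0.096. OR = (0.108/0.892)/(0.096/0.904) = 1.14.

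Worked case with b = 0.10, h = 0.9, l = 0.3: 0.17 and 0.11. OR = (0.17/0.83)/(0.11/0.89) = 1.66.

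| Borderline share b | h = 0.7, l = 0.4 | h = 0.9, l = 0.3 |
|---|---|---|
| 4% | 0.108 vs 0.096: 1.14 | 0.116 vs 0.092: 1.30 |
| 6% | 0.122 vs 0.104: 1.20 | 0.134 vs 0.098: 1.42 |
| 10% | 0.150 vs 0.120: 1.29 | 0.170 vs 0.110: 1.66 |

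If h = l, the odds ratio is 1 whatever b is. The whole effect comes from outcome-informed calls.

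**3. Reach into the primary endpoint**

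The plan's sample size reproduces. For 20% versus 10%, two-sided 0.05 and 80% power, the two-proportion formula with continuity correction gives 219 per group against the stated 220 (199 without correction). Then 220/0.8 = 275.

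Under the table in SAP 7.4.1.1, a patient with IA present is positive whether DSA is positive, negative or indeterminate. A borderline call therefore changes the composite only in patients without IA present. Where IA is absent it moves the patient between positive and negative. Where IA is unknown it moves the patient between positive and indeterminate, and indeterminate patients are excluded from the primary analysis.

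For scale, the planned rates give 220 × 0.20 = 44 and 220 × 0.10 = 22 events. Reversing 8 control-arm positives (8/220 = 3.6% of that arm), with none reversed in the other arm, takes Fisher's exact p from 0.005 to 0.066. Reversing 7 leaves it at 0.0495. That pattern needs calls that depend on arm, which the stated blinding is meant to prevent.

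**4. Would a planned analysis reveal it?**

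Protocol 7.4.1.2 and 7.4.1.3 and SAP 7.4.1.2 vary the analysis set, the imputation or the creatinine status. None uses a DSA definition without adjudication.

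**The case against.** The strongest reply is Protocol 10.2. The Board is independent, blinded to allocation, receives its material for blinded assessment and works to a charter that specifies the documents. That charter may already limit the packet. This stands, and it is why the point is confined to what the Protocol and SAP leave unsaid.

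A reader might go further and infer that half of the primary endpoint is open to treatment-driven calls. The documents do not support that:
- The clinical-data rule covers borderline results only, and nothing says clinical data can override a clear result.
- IA comes from a separate central assay with a locked classifier.
- No text says the Board receives product or dosing information.
- Trough levels would not identify the arm: Protocol 1.2.1 says the same target range applies to both formulations, and 5.1.2 sets one lower limit for both arms.

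Any figure for a shift between arms would rest on invented call rates and on the blinding failing.

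Two further replies have some weight. The risk-factor models are secondary, in a trial that calls itself exploratory, and SAP 7.1 drops regression for outcomes with event rates under 10%, so some models may not be run. A bare cut at MFI 1000 would also miss prozone samples that the Protocol counts as positive after dilution. The proposed rule allows for this.

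None of these replies answers the outcome leak. Blinding to allocation is not blinding to rejection, biopsy or renal function.

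**Conclusion.** The concern holds in a limited form. As written, the rule lets graft outcomes inform borderline DSA calls, and SAP 7.4.2 then relates DSA to those outcomes. This is incorporation bias that the plan permits; it is not shown to have occurred.

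Its size cannot be derived from the documents. The apparent odds ratios of about 1.14 to 1.66 rest on the assumed clear-positive, borderline and call rates, and on the Board seeing rejection status when it decides. The timing of adjudication relative to outcomes is not stated. If calls precede most outcomes, the effect is smaller.

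Bias in the comparison between arms remains a possible, indirect route, confined to borderline calls in patients without IA present. It should not be reported as a demonstrated flaw in the primary analysis.

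Separately, SAP 3.2 gives borderline cases to the panel while SAP 7.4.1.1 credits the laboratory, so it is unclear whose call enters the analysis.

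The change is worth making. If the charter already restricts the packet, citing its terms in the Protocol and SAP would settle the main part.

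**What to change.** 1. **Limit the data.** In the Protocol synopsis, 2.2.1, 5.3.2 and 10.2, in SAP 3.2 and in the charter, state that borderline calls use only laboratory data (MFI across visits and after dilution, bead specificity, donor and recipient typing, pre-transplant serum) and pre-transplant sensitising history. State that formulation, dosing, biopsy, rejection, renal function and IA results are withheld. Give numeric MFI bounds for borderline.
2. **Add a sensitivity analysis.** Rerun the primary endpoint and the DSA risk-factor models with an unadjudicated rule: MFI of at least 1000 neat, or after the Protocol's dilution step. Use dilution results where they exist, because the synopsis and 2.2.1 describe dilution of sub-threshold samples as occurring in certain cases, while 5.3.2 and 5.7.2 state it generally. Leave unchanged the Board's role on pre-formed DSA, on which mFAS membership depends.
3. **Reconcile SAP 3.2 with SAP 7.4.1.1** on who makes the final DSA call.

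The cost is wording in three documents and a few extra model runs on MFI values already collected. The downside is that a few borderline calls are made without post-transplant context. SAP 7.9 reports that the interim analysis is done. Results already adjudicated with clinical data would be covered by the sensitivity analysis and not re-adjudicated.
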